### Exclusion criteria for longitudinal composite scores

The longitudinal composite observations of relative change in LMV are sensitive to low overall LMV. Therefore, criteria are required for exclusion of such observations. To ensure that the relative change in LMV is reliable LMVref needs to fulfill one of the below:

- Be at least 25 cl and consist of measurements from at least 2 muscles.
- Be at least 50 cl with measurements from at least one muscle.

These criteria apply for all longitudinal composite measurements.

- (1) If a subject's individual muscles couldn't fulfil both bullets above, the subject's change from reference time point in longitudinal composite scores for LMV (L), LMV (%), MFF and MFI should be set to missing. Here, LMVref refers to LMV at reference time point, such as reference screening, and cl means 0.01 liter.
- (2) If a subject's individual muscles could fulfil at least one of the two bullets above, the subject's change from reference time point in longitudinal composite scores for LMV (L), LMV (%), MFF and MFI should not be set to missing.
- (3) The first bullet above refers to at least 2 muscles with a combined LMVref (L) of at least 0.25 liter.

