#### **Composite measures:**

Composite variables, incorporating pre-selected muscles, will be derived for longitudinal analysis of muscle fat fraction, lean muscle volume and muscle fat infiltration (MFFtot, LMVtot, and MFItot respectively). The longitudinal composite observations of relative change in LMV are sensitive to low overall LMV, therefore an exclusion criterium is applied for such observations. See [Appendix 6](#) for derivations and exclusion criteria. The scores will be derived and exclusions applied by scientists at the MRI Service Provider (AMRA Medical Inc.).

Descriptive statistics of MFFtot, LMVtot, and MFItot per visit as well as changes from baseline will be presented for the whole body, as well as muscle regions as applicable. Missing visit observations will be back calculated from provided screening and change from screening values.

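### SAP Appendix 6, exclusion rule (1), is misworded: read literally, it blanks the longitudinal MRI composites of subjects whom the lead-in and rule (2) keep

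*SAP*

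**What the plan says.** The exclusion section at the end of SAP Appendix 6 says that, for the relative change in lean muscle volume (LMV) to be reliable, the reference volume LMVref "needs to fulfill one of the below". Two bullets follow:

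- The first bullet reads "Be at least 25 cl and consist of measurements from at least 2 muscles".
- The second bullet reads "Be at least 50 cl with measurements from at least one muscle".

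The section applies these criteria to all longitudinal composites and then gives three numbered rules.

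- Rule (1) directs values to be set to missing. It begins "If a subject's individual muscles couldn't fulfil both bullets above, the subject's change from reference time point in longitudinal composite scores", and it covers the changes in LMV in litres, LMV in percent, muscle fat fraction (MFF) and muscle fat infiltration (MFI).
- Rule (2) is the keeping instruction: "If a subject's individual muscles could fulfil at least one of the two bullets above", the same change scores are not set to missing.
- Rule (3) explains the first bullet: "The first bullet above refers to at least 2 muscles with a combined" reference volume of at least 0.25 litre.

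SAP 3.4.2 summarises the reason for the exclusion, refers to Appendix 6 for the derivations and criteria, and says that the MRI service provider derives the scores and applies the exclusions.

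**The concern.** Rule (1) can be read in two ways. Taken word for word, a subject who fails either bullet has not fulfilled both and is set to missing. Taken loosely, the subject has failed both, that is, has met neither. The two readings differ for anyone who meets exactly one bullet, and for those subjects the literal reading contradicts the lead-in and rule (2).

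At stake is who is counted in the longitudinal composites. Only muscles classed as affected at baseline, with no signal quality problem at either timepoint, enter these sums, so small reference volumes are plausible, particularly for regional composites. A literal rule (1) would blank all four change scores together. SAP 3.4.2 also plans to back-calculate missing visit values from the screening value and the change from screening, and that route is closed where the change has been blanked. The exclusions are applied outside the sponsor, so a sentence that can be coded in two ways deserves a check.

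**Working it through.** The plan states no figure to reproduce, so the check is one of logic.

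**Inputs (SAP Appendix 6).** Let m be the number of muscles contributing and V the reference lean volume in cl. The appendix defines 1 cl as 0.01 litre, so 25 cl is the 0.25 litre of rule (3).

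- A (first bullet): V ≥ 25 and m ≥ 2
- B (second bullet): V ≥ 50 and m ≥ 1
- Lead-in: acceptable if A or B
- Rule (1), literal: missing if not (A and B)
- Rule (1), read as neither: missing if (not A) and (not B)
- Rule (2): keep if A or B

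**Result by case.**

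| Case | A | B | Lead-in and rule (2) | Rule (1), literal | Rule (1), neither |
|---|---|---|---|---|---|
| m ≥ 2, V ≥ 50 | yes | yes | keep | keep | keep |
| m ≥ 2, 25 ≤ V < 50 | yes | no | keep | **missing** | keep |
| m = 1, V ≥ 50 | no | yes | keep | **missing** | keep |
| m = 1, V < 50 | no | no | not acceptable | missing | missing |
| m ≥ 2, V < 25 | no | no | not acceptable | missing | missing |

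For example, 40 cl from two muscles, or 80 cl from one muscle, is kept by rule (2) and dropped by a literal rule (1).

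A grid of 22 combinations (m from 0 to 3; V from 0 to 80 cl, including 24.9, 25, 49.9 and 50) confirms the table. The literal reading conflicts with rule (2) in 8 combinations, all with exactly one bullet met. The neither reading gives 0 conflicts and 0 combinations left undecided. The 8 of 22 describes the grid only and does not estimate the share of subjects affected.

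**Which reading is meant.** Under the literal reading, a subject is kept only if A and B both hold:

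(V ≥ 25 and m ≥ 2) and (V ≥ 50 and m ≥ 1) = (V ≥ 50 and m ≥ 2).

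The 25 cl threshold, the single-muscle allowance and rule (3), which exists only to explain the 25 cl bullet, would then have no effect. Under the neither reading every element does some work, and rules (1) and (2) are exact complements.

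**Size.** Each subject wrongly dropped would be 1/14 = 7.1% of the 14 enrolled (Protocol 4.4). The documents give no reference volumes or muscle counts, so the number meeting exactly one bullet cannot be computed. Logic alone limits it only to between 0 and 14.

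**The case against.** The strongest reply is that the appendix already settles the disputed case. The lead-in asks for one bullet, and rule (2) speaks directly of the subject who "could fulfil at least one of the two bullets above". A programmer would have to follow rule (1) alone and ignore the text on either side of it to go wrong. That stands, and it limits the point to a wording error with a recoverable intent.

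Three stronger readings are tempting, and the documents do not support them.

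- *That Appendix 6 contains two irreconcilable rules and leaves inclusion open.* It does not: one ordinary reading of rule (1) agrees with everything else in the section.
- *That SAP 3.4.2 and Appendix 6 disagree on scope.* SAP 3.4.2 says that the relative LMV changes are "sensitive to low overall LMV, therefore an exclusion criterium is applied for such observations", whereas Appendix 6 also blanks absolute LMV, MFF and MFI. But 3.4.2 goes straight on to refer to Appendix 6 for the criteria and exempts no measure, so it is a summary of the full rule.
- *That subjects have in fact been lost from the MRI results.* Nothing in the documents shows that the literal rule was ever programmed. The individual-muscle summaries and the cross-sectional composites do not depend on it in any case.

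The appendix also does not say whether the test is run once per subject or separately for the whole body and each region, or whether exclusions are counted per composite. Those are details that could usefully be added; they are not errors in the rule.

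What survives is that the rule ordering deletion says something different, taken at its word, from the sentences around it.

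**Conclusion.** The point holds as a minor wording error. Rule (1), read literally, blanks the longitudinal composite changes of subjects who meet exactly one criterion, contrary to the lead-in and rule (2). The intended rule, keeping a subject who meets at least one, can be recovered with confidence from the lead-in, rule (2) and rule (3).

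The consequence is limited. MRI change is an exploratory endpoint (SAP 1.3.3), summarised descriptively in a study without formal statistical tests of treatment effect (SAP 2.4; Protocol 2.3). No primary safety or secondary result depends on it. The number of affected subjects is unknown and may be zero. Any effect on the outputs requires both that some subjects meet exactly one criterion and that the service provider applied rule (1) literally; the documents establish neither.

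**What to change.** In SAP Appendix 6, rule (1), change the condition so that it applies when the subject's muscles fulfil neither of the two bullets. Leave the lead-in, both bullets and rules (2) and (3) as they are. Ask the MRI service provider to confirm in writing that values were set to missing only when neither criterion was met. If that is confirmed, no output changes. If it is not, restore the composite changes of the subjects who meet exactly one criterion and reissue the affected tables.

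The cost is one phrase in the SAP and one query to the provider.

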## APPENDIX 7: NORMALIZATION FOR ELBOW FLEXION, ELBOW EXTENSION, AND SHOULDER ABDUCTION

Douma et al. *BMC Sports Science, Medicine, and Rehabilitation* 2014, **6**:10  
<http://biomedcentral.com/2052-1847/6/10>

### RESEARCH ARTICLE

### Open Access

# Reference values for isometric muscle force among workers for the Netherlands: a comparison of reference values

Rob KW Douma1\*, Remko Soer, Wim P Krijnen, Michiel Reneman and Cees P van der Schans

**Table 4 Dominant and non-dominant muscle strength means (sd) per age group for males**

Muscle force	Age group	Dominant		Non dominant	
		N	Mean(Sd.)	N	Mean (Sd.)
Elbow flexion	20-29	48	281(48)	48	261(49)
	30-39	51	273(50)	51	266(51)
	40-49	70	271(59)	70	261(51)
	50-59	59	259(52)	59	245(47)
Elbow extension	20-29	48	186(38)	48	182(37)
	30-39	51	183(40)	51	179(45)
	40-49	70	185(46)	70	179(44)
	50-59	59	181(37)	59	173(36)
Knee flexion	20-29	48	267(57)	48	252(52)
	30-39	51	262(60)	51	250(55)
	40-49	68	274(77)	69	263(77)
	50-59	59	242(57)	59	234(55)
Knee extension	20-29	47	379(105)	47	371(112)
	30-39	51	351(99)	51	341(101)
	40-49	69	368(114)	70	341(107)
	50-59	59	337(103)	57	335(102)
Shoulder abduction	20-29	14	172(48)	14	173(35)
	30-39	26	181(38)	26	176(40)
	40-49	35	173(43)	35	177(40)
	50-59	37	178(39)	39	177(43)

**Table 5 Dominant and non-dominant muscle strength means (sd) per age group for females**

Female	Muscle force	Dominant		Non dominant	
		Age group	N	Mean(Sd.)	N
Elbow flexion	20-29	51	191(30)	51	183(30)
	30-39	39	195(34)	39	186(35)
	40-49	66	191(37)	66	186(37)
	50-59	34	181(29)	34	166(22)
Elbow extension	20-29	51	132(28)	51	131(28)
	30-39	39	128(24)	39	125(26)
	40-49	66	131(28)	66	125(29)
	50-59	34	120(20)	34	118(27)
Knee flexion	20-29	51	198(38)	51	191(37)
	30-39	39	190(41)	39	188(35)
	40-49	66	190(51)	67	183(52)
	50-59	34	174(42)	34	169(45)
Knee extension	20-29	51	261(80)	51	260(75)
	30-39	38	273(87)	39	264(88)
	40-49	66	262(127)	67	245(79)
	50-59	34	244(66)	34	228(51)
Shoulder abduction	20-29	14	115(19)	14	124(23)
	30-39	22	116(26)	22	118(30)
	40-49	41	119(28)	41	118(26)
	50-59	15	114(22)	15	116(21)

**APPENDIX 8: NORMALIZATION FOR HAND GRIP STRENGTH**

**Jamar® Smart Hand Dynamometer**  
**FROM PATTERSON MEDICAL**

**NORMATIVE GRIP STRENGTH DATA:**

Age	Hand	Males Mean (lbs)	SD	Females Mean (lbs)	SD	Males Mean (kg)	SD	Females Mean (kg)	SD
6-7	R	32.5	4.8	28.6	4.4	14.7	2.2	13.0	2.0
	L	30.7	5.4	27.1	4.4	13.9	2.4	12.3	2.0
8-9	R	41.9	7.4	35.3	8.3	19.0	3.4	16.0	3.8
	L	39	9.3	33	6.9	17.7	4.2	15.0	3.1
10-11	R	53.9	9.7	49.7	8.1	24.4	4.4	22.5	3.7
	L	48.4	10.8	45.2	6.8	22.0	4.9	20.5	3.1
12-13	R	58.7	15.5	56.8	10.6	26.6	7.0	25.8	4.8
	L	55.4	16.9	50.9	11.9	25.1	7.7	23.1	5.4
14-15	R	77.3	15.4	58.1	12.3	35.1	7.0	26.4	5.6
	L	64.4	14.9	49.3	11.9	29.2	6.8	22.4	5.4
16-17	R	94	19.4	67.3	16.5	42.6	8.8	30.5	7.5
	L	78.5	19.1	56.9	14	35.6	8.7	25.8	6.4
18-19	R	108	24.6	71.6	12.3	49.0	11.2	32.5	5.6
	L	93	27.8	61.7	12.5	42.2	12.6	28.0	5.7
20-24	R	121	20.6	70.4	14.5	54.9	9.3	31.9	6.6
	L	104.5	21.8	61	13.1	47.4	9.9	27.7	5.9
25-29	R	120.8	23	74.5	13.9	54.8	10.4	33.8	6.3
	L	110.5	16.2	63.5	12.2	50.1	7.3	28.8	5.5
30-34	R	121.8	22.4	78.7	19.2	55.2	10.2	35.7	8.7
	L	110.4	21.7	68	17.7	50.1	9.8	30.8	8.0
35-39	R	119.7	24	74.1	10.8	54.3	10.9	33.6	4.9
	L	112.9	21.7	66.3	11.7	51.2	9.8	30.1	5.3
40-44	R	116.8	20.7	70.4	13.5	53.0	9.4	31.9	6.1
	L	112.8	18.7	62.3	13.8	51.2	8.5	28.3	6.3
45-49	R	109.9	23	62.2	15.1	49.8	10.4	28.2	6.8
	L	100.8	22.8	56	12.7	45.7	10.3	25.4	5.8
50-54	R	113.6	18.1	65.8	11.6	51.5	8.2	29.8	5.3
	L	101.9	17	57.3	10.7	46.2	7.7	26.0	4.9
55-59	R	101.1	26.7	57.3	12.5	45.9	12.1	26.0	5.7
	L	83.2	23.4	47.3	11.9	37.7	10.6	21.5	5.4
60-64	R	89.7	20.4	55.1	10.1	40.7	9.3	25.0	4.6
	L	76.8	20.3	45.7	10.1	34.8	9.2	20.7	4.6
65-69	R	91.1	20.6	49.6	9.7	41.3	9.3	22.5	4.4
	L	76.8	19.8	41	8.2	34.8	9.0	18.6	3.7
70-74	R	75.3	21.5	49.6	11.7	34.2	9.8	22.5	5.3
	L	64.8	18.1	41.5	10.2	29.4	8.2	18.8	4.6
75+	R	65.7	21.	42.6	11	29.8	9.5	19.3	5.0
	L	55	17	37.6	8.9	24.9	7.7	17.1	4.0

## APPENDIX 9: SAS CODE FOR QMT PREDICTED PERCENT SCORES

SAS code below provided by [REDACTED] (Fulcrum) and [REDACTED]:

Below codes creates QMT predicted standardized scores for each QMT muscles:

```
*if medmax^.5 then mm=(medmax+1); * Per [name] 6/26/95;  
mm=medmax+1;  
  
mdflp=4.6332- (0.00241*age)+(0.00607*height);  
fdflp=4.3991- (0.00241*age)+(0.00607*height);  
mdfrp=4.9847- (0.00277*age)+(0.00435*height);  
fdfrp=4.6962- (0.00277*age)+(0.00435*height);  
mdtlp=4.5529- (0.00522*age)+(0.00569*height);  
fdtlp=1.7941- (0.00522*age)+(0.01910*height);  
mdtrp=4.6812- (0.00650*age)+(0.00518*height);  
fdtrp=2.2375- (0.00650*age)+(0.01663*height);  
meelp=3.7628- (0.00151*age)+(0.00864*height);  
feelp=3.2676- (0.00151*age)+(0.00864*height);  
meerp=4.0617- (0.00232*age)+(0.00737*height);  
feerp=3.5597- (0.00232*age)+(0.00737*height);  
meflp=4.1605- (0.00266*age)+(0.00863*height);  
feflp=2.8467- (0.00266*age)+(0.01442*height);  
mefrp=5.0254- (0.00335*age)+(0.00430*height);  
fefrp=3.1534- (0.00335*age)+(0.01298*height);  
merlp=3.8313- (0.00365*age)+(0.00714*height);  
ferlp=3.3893- (0.00365*age)+(0.00714*height);  
merrp=3.9446- (0.00245*age)+(0.00625*height);  
ferrp=3.5009- (0.00245*age)+(0.00625*height);  
mhblp=3.6885- (0.00188*age)+(0.00960*height);  
fhblp=1.7266- (0.00188*age)+(0.01884*height);  
mhbrp=4.6122- (0.00258*age)+(0.00499*height);  
fhbrp=1.9143- (0.00258*age)+(0.01834*height);  
mhdlp=4.3537- (0.00331*age)+(0.00930*height);  
fhdlp=3.8317- (0.00331*age)+(0.00930*height);  
mhdrp=5.2077- (0.00387*age)+(0.00477*height);  
fhdrp=4.5916- (0.00387*age)+(0.00477*height);
```

```
mkelp=5.1832- (0.00837*age)+(0.00789*height);  
fkelp=4.7644- (0.00837*age)+(0.00789*height);  
mkerp=6.4124- (0.00701*age)+(0.00104*height);  
fkerp=3.4479- (0.00701*age)+(0.01557*height);  
mkflp=4.9876- (0.00591*age)+(0.00499*height);  
fkflp=2.1190- (0.00591*age)+(0.01994*height);  
mkfrp=4.9481- (0.00641*age)+(0.00524*height);  
fkfrp=2.0670- (0.00641*age)+(0.02020*height);  
mlgrip = -26.9062 - (0.1329 * age) + (0.4374 * height);  
flgrip = -39.5766 - (0.1329 * age) + (0.4374 * height);  
mrgrip = -9.7022 - (0.1732 * age) + (0.3696 * height);  
frgrip = -24.8027 - (0.1732 * age) + (0.3696 * height);
```

```
if (test='DFL' and sex='M') then stanqmt=(log(mm)-mdflp)/0.20454;  
if (test='DFL' and sex='F') then stanqmt=(log(mm)-fdflp)/0.20454;  
if (test='DFR' and sex='M') then stanqmt=(log(mm)-mdfrp)/0.20380;  
if (test='DFR' and sex='F') then stanqmt=(log(mm)-fdfrp)/0.20380;  
if (test='SBL' and sex='M') then stanqmt=(log(mm)-mdtlp)/0.24541;*;  
if (test='SBL' and sex='F') then stanqmt=(log(mm)-fdtlp)/0.24541;*;  
if (test='SBR' and sex='M') then stanqmt=(log(mm)-mdtrp)/0.27474;*;  
if (test='SBR' and sex='F') then stanqmt=(log(mm)-fdtrp)/0.27474;*;  
if (test='EEL' and sex='M') then stanqmt=(log(mm)-meelp)/0.19315;  
if (test='EEL' and sex='F') then stanqmt=(log(mm)-feelp)/0.19315;  
if (test='EER' and sex='M') then stanqmt=(log(mm)-meerp)/0.17903;  
if (test='EER' and sex='F') then stanqmt=(log(mm)-feerp)/0.17903;  
if (test='EFL' and sex='M') then stanqmt=(log(mm)-meflp)/0.14704;  
if (test='EFL' and sex='F') then stanqmt=(log(mm)-feflp)/0.14704;  
if (test='EFR' and sex='M') then stanqmt=(log(mm)-mefrp)/0.14746;  
if (test='EFR' and sex='F') then stanqmt=(log(mm)-fefrp)/0.14746;  
if (test='ERL' and sex='M') then stanqmt=(log(mm)-merlp)/0.20397;  
if (test='ERL' and sex='F') then stanqmt=(log(mm)-ferlp)/0.20397;  
if (test='ERR' and sex='M') then stanqmt=(log(mm)-merrp)/0.19397;  
if (test='ERR' and sex='F') then stanqmt=(log(mm)-ferrp)/0.19397;  
if (test='HBL' and sex='M') then stanqmt=(log(mm)-mhblp)/0.20715;  
if (test='HBL' and sex='F') then stanqmt=(log(mm)-fhblp)/0.20715;  
if (test='HBR' and sex='M') then stanqmt=(log(mm)-mhbrp)/0.23012;
```

```
if (test='HBR' and sex='F') then stanqmt=(log(mm)-fhbrp)/0.23012;
if (test='HDL' and sex='M') then stanqmt=(log(mm)-mhdlp)/0.21990;
if (test='HDL' and sex='F') then stanqmt=(log(mm)-fhdlp)/0.21990;
if (test='HDR' and sex='M') then stanqmt=(log(mm)-mhdrp)/0.23142;
if (test='HDR' and sex='F') then stanqmt=(log(mm)-fhdrp)/0.23142;
if (test='KEL' and sex='M') then stanqmt=(log(mm)-mkelp)/0.21727;
if (test='KEL' and sex='F') then stanqmt=(log(mm)-fkelp)/0.21727;
if (test='KER' and sex='M') then stanqmt=(log(mm)-mkerp)/0.23823;
if (test='KER' and sex='F') then stanqmt=(log(mm)-fkerp)/0.23823;
if (test='KFL' and sex='M') then stanqmt=(log(mm)-mkflp)/0.19632;
if (test='KFL' and sex='F') then stanqmt=(log(mm)-fkflp)/0.19632;
if (test='KFR' and sex='M') then stanqmt=(log(mm)-mkfrp)/0.21062;
if (test='KFR' and sex='F') then stanqmt=(log(mm)-fkfrp)/0.21062;

if (test = 'HGL' and sex = 'M') then stanqmt = (medmax - mlgrip) / 5.25987;
if (test = 'HGL' and sex = 'F') then stanqmt = (medmax - flgrip) / 5.25987;
if (test = 'HGR' and sex = 'M') then stanqmt = (medmax - mrgrip) / 5.73428;
if (test = 'HGR' and sex = 'F') then stanqmt = (medmax - frgrip) / 5.73428;

drop mm mdflp--frgrip;
```

Below codes created predicted scores

```
predict2=2.71828**predict;
*Percent=(medmax/predict2)*100;
logmm=log(medmax+1);
if sex='M' then do;

if test='DFL' then predict=mdflp;
else if test='DFR' then predict=mdfrp;
else if test='SBL' then predict=mdtlp;
else if test='SBR' then predict=mdtrp;
else if test='EEL' then predict=meelp;
else if test='EER' then predict=meerp;
else if test='EFL' then predict=meflp;
```

```
else if test='EFR' then predict=mefrp;
else if test='ERL' then predict=merlp;
else if test='ERR' then predict=merrp;
else if test='HBL' then predict=mhblp;
else if test='HBR' then predict=mhbrp;
else if test='HDL' then predict=mhdlp;
else if test='HDR' then predict=mhdrp;
else if test='KEL' then predict=mkelp;
else if test='KER' then predict=mkerp;
else if test='KFL' then predict=mkflp;
else if test='KFR' then predict=mkfrp;
  else if test='HGR' then predict=mrgrip;
  else if test='HGL' then predict=mlgrip;
end;

else if sex='F' then do;
  if test='DFL' then predict=fdflp;
  else if test='DFR' then predict=fdfrp;
  else if test='SBL' then predict=fdtlp;
  else if test='SBR' then predict=fdtlp;
  else if test='EEL' then predict=feelp;
  else if test='EER' then predict=feerp;
  else if test='EFL' then predict=feflp;
  else if test='EFR' then predict=fefrp;
  else if test='ERL' then predict=ferlp;
  else if test='ERR' then predict=ferrp;
  else if test='HBL' then predict=fhblp;
  else if test='HBR' then predict=fhbrp;
  else if test='HDL' then predict=fhdlp;
  else if test='HDR' then predict=fhdrp;
  else if test='KEL' then predict=fkelp;
  else if test='KER' then predict=fkerp;
  else if test='KFL' then predict=fkflp;
  else if test='KFR' then predict=fkfrp;
  else if test='HGR' then predict=frgrip;
  else if test='HGL' then predict=flgrip;
end;
```

```
*predict2=2.71828**predict;
*Percent=(medmax/predict2)*100;
*logmm=log (medmax+1);
```

Below codes creates overall percent predicted and standardized scores for each muscles:

\*Multiply each muscle to 9.8 and convert to newton;

```
data qma2; set qma;length test $5;
Test='SBL'; MedMax=9.8*SAL; output;
Test='SBR'; MedMax=9.8*SAR; output;

Test='EFL'; MedMax=9.8*EFL; output;
Test='EFR'; MedMax=9.8*EFR; output;

Test='EEL'; MedMax=9.8*EEL; output;
Test='EER'; MedMax=9.8*EER; output;

Test='DFL'; MedMax=9.8*ADL; output;
Test='DFR'; MedMax=9.8*ADR; output;

Test='KFL'; MedMax=9.8*KFL; output;
Test='KFR'; MedMax=9.8*KFR; output;

Test='KEL'; MedMax=9.8*KEL; output;
Test='KER'; MedMax=9.8*KER; output;

Test='HGL'; MedMax=HGL; output;*hand grip stays in kg;
Test='HGR'; MedMax=HGR; output;

keep record_id redcap_event_name  sex age height  test medmax  ;
run;
*proc print; run;
```

\*creates percent and standardized scores;

```
data qma3; set qma2;
%include 'n:\research\FSH\qmt_stan_updated.sas';
%include 'n:\research\ibm\predict.sas';
predict2=2.71828**predict;
if test='SBL' OR TEST='SBR' OR TEST='EFL' OR TEST='EFR' OR TEST='EEL' OR TEST='EER' or
test='DFL' OR TEST='DFR'
OR TEST='KFL' OR TEST='KFR' OR TEST='KER' OR TEST='KEL' or test='DFL' or test='DFR'
THEN Percent=(medmax/predict2)*100;
if test='HGR' or test='HGL' then percent=(medmax/predict)*100;
logmm=log (medmax+1);run;
```

```
proc sort data=qma3;by record_id redcap_event_name ;run;
proc means data=qma3 nopol; by record_id redcap_event_name ;
var stanqmt percent age;
output out=qmameans mean=;
label stanqmt='Standartized Overall QMT Score(SA, EF, EE, AD,KF,KE,HG)';
label percent='QMT:Overall Percent Predicted(SA, EF, EE, AD,KF,KE,HG) ';
run;
```

\*Below codes calculates Lower Extremity QMA standardized and percent scores;

```
data qma2u; set qma;
Test='SBL'; MedMax=9.8*SAL; output; ****;
Test='SBR'; MedMax=9.8*SAR; output; ****;

Test='EFL'; MedMax=9.8*EFL; output;
Test='EFR'; MedMax=9.8*EFR; output;

Test='EEL'; MedMax=9.8*EEL; output;
Test='EER'; MedMax=9.8*EER; output;
```

```
Test='HGL'; MedMax=HGL; output;
Test='HGR'; MedMax=HGR; output;

keep record_id redcap_event_name sex age height test
medmax ;
run;

data qma3u; set qma2u;
%include 'n:\research\FSH\qmt_stan_updated.sas';
%include 'n:\research\ibm\predict.sas';
predict2=2.71828**predict;
if test='SBL' OR TEST='SBR' OR TEST='EFL' OR TEST='EFR' OR TEST='EEL' OR TEST='EER' THEN ;
Percent_upper=(medmax/predict2)*100;
if test='HGR' or test='HGL' then percent_upper=(medmax/predict)*100;
logmm=log(medmax+1);
run;

data qma3u;set qma3u(rename=(stanqmt=stanqmt_upper));
run;

proc sort data=qma3u;by record_id redcap_event_name ; ;run;
proc means data=qma3u noprint; by record_id redcap_event_name ;
var stanqmt_upper percent_upper age;
output out=qmameans_upper mean=;
run;
data qmameans_upper;set qmameans_upper;
label stanqmt_upper='Standardized Upper Extremity QMT Score(SA,EF,EE,HG)';
label percent_upper=' Upper Extremity Percent Predicted QMT Score(SA,EF,EE,HG)';run;

*Below codes calculates Lower Extremity QMA standardized and percent scores;
data qma2l; set qma;

Test='DFL'; MedMax=9.8*ADL; output; ****;
Test='DFR'; MedMax=9.8*ADR; output; ****;

Test='KFL'; MedMax=9.8*KFL; output;
```

```
Test='KFR'; MedMax=9.8*KFR; output;

Test='KEL'; MedMax=9.8*KEL; output;
Test='KER'; MedMax=9.8*KER; output;

keep record_id redcap_event_name sex age height test
medmax ;
run;

data qma31; set qma21;
%include 'n:\research\FSH\qmt_stan_updated.sas';
%include 'n:\research\ibm\predict.sas';
predict2=2.71828**predict;
Percent_leg=(medmax/predict2)*100;
logmm=log (medmax+1);run;

data qma31;set qma31(rename=(stanqmt=stanqmt_leg));
run;

proc sort data=qma31;by record_id redcap_event_name date40; ;run;
proc means data=qma31 noprint; by record_id redcap_event_name ;
  var stanqmt_leg percent_leg age;
  output out=qmameans_leg mean=;
run;
data qmameans_leg;set qmameans_leg;
label stanqmt_leg='Standardized Lower Extremity QMT Score(AD, KF, KE)';
label percent_leg='Lower Extremity Percent Predicted QMT Score(AD, KF, KE)';run;

*Merge the original qmt enties , overall qma , lower and upper qma means;

data
merge qmt qmameans qmameans_upper qmameans_leg;by record_id redcap_event_name ;run;
```

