#### **3.4.8 Dynamometry**

Dynamometry measures the static muscle strength without any movement. Manual dynamometry with hand-held devices and quantitative myometry testing (QMT) with bedframe equipment will be used to assess the skeletal muscle strength of study subjects in both the upper and lower limbs bilaterally. Manual dynamometry be assessed at Screening, Week 4, Week 14, Week 24, Week 48, and End of Treatment (Week 60). QMT will be assessed at Screening, Week 4, and End of Treatment (Week 60).

Descriptive statistics for percent predicted QMT as well as change from baseline will be presented for: (a.) all muscles combined; (b.) upper extremity strength, which includes the hands, shoulders and elbows combined; and (c.) lower extremity strength, which includes knee extension, knee flexion, and ankle dorsiflexors combined. Percent predicted QMT scores will be calculated using SAS® code provided in [Appendix 9](#) (with additional extremity details in [Appendix 10](#)).

Descriptive statistics for total manual dynamometry as well as change from baseline will be presented for: (a.) all muscles combined; (b.) upper extremity strength, which includes the hands, shoulders and elbows combined; and (c.) lower extremity strength, which includes right and left ankle dorsiflexors combined. Raw scores will be presented.

Descriptive statistics of manual dynamometry average and maximum weight in kilogram per visit as well as the change from baseline and percent change from baseline will be presented according to assessment (dominant shoulder abductors, non-dominant shoulder abductors, dominant elbow flexors, non-dominant elbow flexors, dominant elbow

extensors, non-dominant elbow extensors, dominant hand grip, non-dominant hand grip, right ankle dorsiflexors, and left ankle dorsiflexors). Raw scores will be presented.

Descriptive statistics of normalized manual dynamometry average and maximum weight in kilogram per visit as well as the change from baseline will be presented by overall upper extremity and according to assessment (dominant shoulder abductors, non-dominant shoulder abductors, dominant elbow flexors, non-dominant elbow flexors, dominant elbow extensors, non-dominant elbow extensors, dominant hand grip, and non-dominant hand grip).

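### As printed, the SAP's percent-predicted QMT code scores women's right shoulder against the left-shoulder equation

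*SAP*

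**What the plan says.** SAP Section 3.4.8 separates hand-held dynamometry from "quantitative myometry testing (QMT) with bedframe equipment". The bed-frame measure is taken at Screening, Week 4 and Week 60. It is summarised descriptively as percent predicted, with change from baseline, for all muscles, the upper extremity and the lower extremity. The section refers to Appendix 9 for the calculation and gives no separate formula in words.

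Appendix 9 defines two shoulder equations for women, both on the log scale:

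- left: "fdtlp=1.7941- (0.00522*age)+(0.01910*height"
- right: "fdtrp=2.2375- (0.00650*age)+(0.01663*height"

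The standardized-score code uses the right-side equation for the right shoulder: "if (test='SBR' and sex='F') then stanqmt=(log(mm)-fdtrp)/0.27474". In the percent-predicted code, the male block does the same: "else if test='SBR' then predict=mdtrp". The female block has "else if test='SBL' then predict=fdtlp" for the left shoulder and then "else if test='SBR' then predict=fdtlp" for the right.

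**The concern.** `SBR` is the right shoulder: Appendix 9 fills it from `SAR`, which Appendix 10 labels as right shoulder abduction. As printed, a woman's right shoulder is therefore standardized against one equation and expressed as percent predicted against another. In the female percent-predicted block `fdtrp` is never used. Nothing in the SAP suggests that this is intended.

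The two equations differ in intercept, age slope and height slope. The error therefore varies with age and height and changes sign, so a reader could not remove it with a constant. What is at stake is the level of two descriptive composites in women: the upper extremity (1 of 8 tests) and overall (1 of 14 tests).

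**Working it through.** **Side check.** Each sex block has 20 lines that assign an equation to a test, 40 in all. In 39 the side of the test matches the side of the equation. The female `SBR` line is the exception.

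**Inputs.** The two female shoulder equations and the percent formula (100 × measured force ÷ exponentiated prediction) come from Appendix 9. Ages 18 to 65 come from Protocol Section 4.2. Heights of 150 to 185 cm are an assumption, because the documents give none.

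**Unit of height.** Appendix 9 does not state it. The women's left-grip equation, "flgrip = -39.5766 - (0.1329 * age) + (0.4374 * height", settles the matter for a woman of 45:

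- height 165: -39.5766 - 0.1329×45 + 0.4374×165 = 26.6 kg
- height 65: -39.5766 - 0.1329×45 + 0.4374×65 = -17.1 kg

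A negative grip is impossible, so inches cannot be meant and centimetres fit.

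**Ratio of printed to intended percent predicted.** The measured force cancels, leaving

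exp(`fdtrp` - `fdtlp`) = exp(0.4434 - 0.00128×age - 0.00247×height).

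| Age, height | Exponent | Ratio | Error in right-shoulder percent predicted |
|---|---|---|---|
| 18 y, 150 cm | 0.4434 - 0.02304 - 0.3705 = 0.04986 | 1.0511 | +5.1% |
| 45 y, 165 cm | 0.4434 - 0.0576 - 0.40755 = -0.02175 | 0.9785 | -2.15% |
| 65 y, 185 cm | 0.4434 - 0.0832 - 0.45695 = -0.09675 | 0.9078 | -9.2% |

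The first and last rows are the extremes over the range. At 45 y the ratio is 1.0030, 0.9906, 0.9665 and 0.9546 at 155, 160, 170 and 175 cm.

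**Composite level.** Each composite is the plain mean of its tests. At a true 50% of predicted with every test present, the error is 50×(ratio - 1)/8 for the upper extremity and 50×(ratio - 1)/14 overall.

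| Age, height | Upper extremity (points) | Overall (points) |
|---|---|---|
| 18 y, 150 cm | +0.320 | +0.183 |
| 45 y, 165 cm | -0.134 | -0.077 |
| 65 y, 185 cm | -0.576 | -0.329 |

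**Change from baseline.** Suppose every test falls from 50% to 48%, a true change of -2.00. With age held fixed the upper-extremity change is (-14 - 2×ratio)/8. At 65 y, 185 cm this is (-14 - 1.816)/8 = -1.977. If age advances one year, the follow-up ratio is multiplied by exp(-0.00128). At 18 y, 150 cm the right-shoulder change is then 48×1.0498 - 50×1.0511 = -2.17, and the composite change is (-14 - 2.17)/8 = -2.021. Those are the extremes, so the range is -2.021 to -1.977 for the upper extremity. The corresponding overall range is -2.012 to -1.987.

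**Group means.** Protocol Section 4.1 gives 14 subjects but no split by sex, so the shift in the group mean cannot be computed. As an illustration only, 7 women of 45 y and 165 cm at 50% of predicted would move the group means by -0.134×7/14 = -0.067 (upper extremity) and -0.077×7/14 = -0.038 (overall).

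**The case against.** The strongest reply is that this may not be an error in the SAP at all. It rests on one letter in machine-read text, directly below an identical token, and Appendix 9 has other character-level slips as extracted: a data set is created as `qma2l` and then read as `qma21`. Those slips do not swap l and r, and `fdtrp` was read correctly where it is defined and where the standardized score uses it. A misread is therefore possible but not shown.

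The second reply is that the printed block may not be what ran. The scoring steps include an external `predict.sas`, which is not reproduced, and the printed fragment computes the exponentiated prediction before the prediction is assigned. This stands: no computed score can be called wrong from the documents. The printed block is nevertheless the only specification of the mapping that a reader has.

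The third reply is that the effect is negligible. That is largely right. The -9.2% end needs a 65-year-old woman 185 cm tall. Bed-frame QMT is descriptive, the listed exploratory endpoint is manual dynamometry, and QMT is not among the sensitivity endpoints of SAP Section 3.6.

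One qualification belongs with the figures. The composite errors assume 50% of predicted and complete tests. The error scales with the score: at 100% of predicted it would be 100×(0.9078 - 1)/8 = -1.15 points for the upper extremity at 65 y, 185 cm. It is also larger when tests are missing, because the mean is taken over those present.

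**Conclusion.** The concern holds as a minor correction. As printed, Appendix 9 contradicts itself on one line, and Section 3.4.8 makes that code the method. If followed, it misstates women's right-shoulder percent predicted and, through it, the upper-extremity and overall levels by the amounts above. Those amounts rest on the assumed height range, height in centimetres, 50% of predicted and complete tests. The group-mean shift cannot exceed the largest error in any one woman under the same conditions.

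Men's scores, lower-extremity scores and standardized scores are unaffected, and change from baseline is nearly so. No primary, secondary or safety result depends on this. Confidence is medium, because neither a misread letter nor a correct executed file can be excluded from the documents.

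**What to change.** 1. Look at the line in the source PDF of the SAP. If it reads `fdtrp`, the point closes.
2. If it reads `fdtlp`, change the female `SBR` assignment to `predict=fdtrp`.
3. In that case, check the same line in the executed `predict.sas`. Only if it has the same assignment, recompute women's right-shoulder percent predicted and re-run the upper-extremity and overall percent-predicted QMT summaries.

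The cost is one look at a page, a one-token correction and one file check, with two descriptive summaries re-run at most.
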